Arabic speaking people including Syrians under the temporary protection of Republic of Turkey and other Arabic speaking immigrants and asylum seekers who screen positive at the General Health Questionnaire (≥ 3) and without a formal diagnosis of any psychiatric disorders according to the M.I.N.I. International Neuropsychiatric Interview (M.I.N.I.) will enter the study. After random allocation they will receive the 5-session SH+ or the ETAU. Assessments will be performed by masked members of the research team immediately after intervention, at 6 months (primary outcome), and a 12 months after randomization.

Time frame

The recruitment phase will last 12 months. After the screening, eligible participants will be assessed at baseline before randomization, immediately post-intervention, and at 6- and 12-monthsfollow-up. The SH+ intervention delivery will be conducted in around 5 weeks (1 session per week).

Expected outcomes

The expected outcomes are a reduction in the incidence of psychiatric diagnoses at 6-month follow-up, and a general improvement in mental health symptoms, psychological functioning, well-being, and economic outcomes at each assessment, in refugees in the SH+ intervention arm, as compared to ETAU.

GENERAL INFORMATION

Project title:

RE-DEFINE: Refugee Emergency – DEFining and Implementing Novel Evidence-based psychosocial interventions

Name of the sponsor/funder:

European Commission, H2020-SC1-2016-2017, topic: SC1-HCO-07-2017, project ID: 779255. The study sponsor has no role in study design; collection, management, analysis, and interpretation of data; writing of the report; and the decision to submit the report for publication. The study sponsor had no ultimate authority over any of the listed activities.

Name and title of the investigators:

[name], PhD

Coordinator

World Health Organization (WHO)

Department of Mental Health and Substance Abuse

[name]

[name] Email: [contact] [contact]

Responsibility: Responsible Officer within WHO for the study

[name], DClinPsy

Technical Officer

World Health Organization (WHO)

Department of Mental Health and Substance Abuse

[name]

[name] SEP

Email: [contact] [contact]

Responsibility: WHO focal point for the study

[name]

Professor of Psychiatry,

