The member of the research team will have no responsibility in checking that refugees actually follow the suggested clinical pathway. Psychiatric care costs will be covered in accordance with the local healthcare system. Given the limited services and transient nature of some refugees in Turkey, it will not be possible for the research team to always check if Syrian refugees actually follow the suggested clinical pathway. Local healthcare systems will cover psychiatric care costs. An SOP will define in detail how the referral to mental health care services will be conducted.

Trial phase *Pilot phase*

Before starting the study we will conduct a preliminary pilot phase with 3-4 participants for each site. This phase will allow testing different aspects related to the delivery of the intervention and assessments, feasibility, and time, prior to the performance of the trial. Participants of the pilot study will not be included in the final sample size. However, they will receive the experimental condition, and a close monitoring of their psychological status through two psychological assessments (one at baseline, and one at the end of the intervention). These assessments will be composed of the same instruments that will be used in the fully-powered trial.

Trial phase assessment

Assessments will take place at screening, at baseline (before random allocation), post-intervention (0-1 week after intervention), and at 6- and 12- months after randomization. The assessments at 6- and 12- months will be performed in person or by telephone/videoconferencing, to ensure the required rates of follow up. Telephone or online assessment and counselling has been used in a range of studies, with a critical review concluding that findings to date are positive and online counselling can have a similar impact and replicate the therapeutic conditions found in face-to-face encounters¹. In addition, a previous study has shown that a mixture of online and telephone based assessments for inclusion in a remote writing based intervention for Post Traumatic Stress Disorder (PTSD) can be feasibly implemented with war traumatised individuals in Iraq². This approach is continuing to be used widely (http://ilajnafsy.bzfo.de/portal/en/)

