Together, these findings suggest that remote therapy and thus assessment can be safely and feasibly applied. The use of audio/video communication will be piloted and used should the pilot show that this can be done safely and feasibly. For the Turkey site, audio/video assessments may be used for both screening and assessments).

Methods of assessment will be recorded, and if necessary, accounted for in the analyses. See Appendix 8 for copies of all screening and outcome measures.

Version 4.1 11 March 2019 12

-

¹ Richards, D. and Viganó, N. (2013), Online Counseling: A Narrative and Critical Review of the Literature. J. Clin. Psychol., 69: 994–1011. doi:10.1002/jclp.21974

² Knaevelsrud C, Brand J, Lange A, Ruwaard J, Wagner B. Web-Based Psychotherapy for Posttraumatic Stress Disorder in War-Traumatized Arab Patients: Randomized Controlled Trial J Med Internet Res 2015;17(3):e71

At baseline, socio-demographic data including sex, age, country of origin, education, religion, marital status and work status will be collected using an ad-hoc form developed specifically for RE-DEFINE. The form will also collect information on education, housing, employment opportunities in Turkey (as measures to improve social integration). Information on the adverse life events and environmental stressors will be collected using the Harvard Trauma Questionnaire Part A (HTQ) (30) and the Post-Migration Living Difficulties (PMLD) and the Recovery Environment (31). We will administer the HTQ Part A (30), in which respondents are asked whether they have experienced each of the events, and a 17-item Checklist for Post-Migration Living Difficulties (PMLD) (31).

In addition, the following assessment scales will be administered (as reported in Table 1 below and Appendix 7 assessment schedule):

- 1. baseline: ad-hoc recruitment form, WHODAS 2.0, PHQ-9, WHO-5 Wellbeing index, PSYCHLOPS, HTQ Part A, PCL-5, EQ-5D-3L, and CSSRI-EU (adapted);
- 2. post-intervention: GHQ-12, M.I.N.I., WHODAS 2.0, PHQ-9, WHO-5 Wellbeing index, PSYCHLOPS, PMLD, and PCL-5;
- 3. 6-month follow-up: GHQ-12, M.I.N.I., WHODAS 2.0, PHQ-9, WHO-5 Wellbeing index, PSYCHLOPS, PMLD, PCL-5, EQ-5D-3L, and CSSRI-EU (adapted);
- 4. 12-month follow up: GHQ-12, M.I.N.I., WHODAS 2.0, PHQ-9, WHO-5 Wellbeing index, PSYCHLOPS, PMLD, PCL-5, EQ-5D-3L, and CSSRI-EU (adapted).

Table 1 Overview of measures that will be administered during the study

Concept	Screening	Baseline	Post- intervention	6-month follow-up	12-month follow-up

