- GHQ-12 post-intervention, at 6- and 12-months follow-up;
- Proportion of participants with a psychiatric diagnosis (M.I.N.I.) post-intervention and at 12 months of follow-up;
- WHODAS 2.0 post-intervention, at 6- and 12-months follow-up;
- PHQ-9 post-intervention, at 6 and 12 months of follow-up;
- WHO-5 Wellbeing index post-intervention, at 6 and 12 months of follow-up;
- PSYCHLOPS post-intervention, at 6 and 12 months of follow-up;
- EQ-5D-3L: at 6 and 12 months of follow-up;
- PCL-5 post-intervention, at 6 and 12 months of follow-up;
- CSSRI-EU (adapted) at 6 and 12 months of follow-up;
- Proportion of participants leaving the study early (dropouts).

Proportion of participants with a psychiatric diagnosis (M.I.N.I.) post-intervention and at 12 months of follow-up

The proportion of participants with a diagnosis of any mental disorder post-intervention and at 12-months of follow-up will be compared between the two groups through the chi-square test. A multivariate analysis will be performed through a Poisson regression model, with a robust error variance, to estimate relative risks directly and to explore the potential confounding effect of prognostic factors, and the interactions with treatment (57).

GHQ-12, WHODAS 2.0, PHQ-9, WHO-5 Wellbeing index, PSYCHLOPS, PCL-5 post-intervention, at 6- and 12- months of follow-up

For each questionnaire, in case of missing items, the Corrected Item Mean Substitution method (58), will be used (i.e. the item mean across participants weighted by the subject's mean of completed items), using information from subjects belonging to the same treatment arm for the same follow-up time.

The hypothesis that the experimental intervention has no effect on GHQ-12, WHODAS 2.0, PHQ-9, WHO-5 Wellbeing index, PSYCHLOPS, PCL-5 scores will be tested by performing seemingly unrelated regression (59), for each follow-up, controlling for baseline values. In case of joint statistical significance of the coefficients related to treatment status, the effect of treatment on each score will be evaluated through appropriate statistical methods for repeated measurements.

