Comprehensive use of annual health and social care resources will be assessed by means of completing the adapted CSSRI-EU at baseline and at 6-month follow-up. Information on the unit-costs of the used services will be gained by the cost compilation for the UK health and social care system (Curtis & Burns, 2017). For services not listed in the UK compilation, price lists, fee charges, reimbursement claims and other sources will be used to identify unit costs. Costs of informal services provided by relatives or volunteers will be estimated on the basis of average salaries per hour. Total direct costs of service use will be calculated by multiplying service units with unit costs. Six months costs from the two surveys will be added to annual costs. Productivity losses will be estimated for asylum seekers and refugees with work permissions by means of the human capital approach (Brouwer & Koopmanschap, 1998) on the basis of group-specific average salaries. All costs will be calculated in 2017 UK £.

Total costs of health and social care use including costs of the SH+ implementation will be investigated with regard to the cost driving effects of asylum seekers and refugees characteristics and the impact of different levels of coverage, different macroeconomic, social and health care indicators by estimating regression based cost functions (Knapp, 1998).

Incremental cost-effectiveness ratios (ICER) will be calculated for the additional costs of gaining one quality-adjusted life year (QALY) by implementing SH+ compared to standard care. QALYs will be estimated on the basis of EQ-5D-3L using country specific utility scores (Szende, Janssen, & Cabases, 2014). The stochastic uncertainty of the ICER will be estimated by nonparametric bootstrapping with 2000 replications. Maximum willingness to pay necessary for a 95 % probability of the SH+ intervention to be cost-effective at a MWTP range between UK£ 0 and 50,000 will be estimated by means of the cost-effectiveness acceptability curve based on the net-monetary-benefit approach (Glick, 2010). Net-monetary benefit (NMB) for each participant will be computed as the QALY gain per patient (QALY) multiplied by the maximum willingness to pay (MWTP) for one QALY minus the direct or

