total costs (C) per patient (NMB_i = QALY_i*MWTP-C_i) for a MWTP range between UK£ 0 and 50,000 in increments of UK£ 5,000 (Hoch et al., 2002). Incremental NMB will be computed by regressing the NMB on study group (Hoch, Briggs, & Willan, 2002). Results of ICEA will be interpreted according to UK MWTP thresholds recommended by the NICE (Appleby, 2016) and alternatively by country specific thresholds provided by (Woods, Revill, Sculpher, & Claxton, 2016).

Interim analyses

No interim analysis is planned for this trial.

Individual Participant Data meta-analysis

Anonymized Individual Participant Data (IPD) from this study will be re-analysed in an IPD meta-analysis collecting IPD from all available trials on SH+. An ad-hoc protocol for the IPD meta-analysis will be developed.

This secondary analysis of data (IPD meta-analysis) will be mentioned in the informed consent form for participants.

QUALITY ASSURANCE

Participants in the study may directly benefit from their participation in the SH+ intervention, which is based on AMBT techniques that are empirically supported. Their participation will furthermore inform adaptation of the SH+ manual into multiple languages, and thus improve knowledge about delivering mental health interventions in the study areas. Since SH+ is non-pharmacological and there is a broad evidence base for its use, it is unlikely that adverse effects due to the intervention will occur. Adverse events will be responded to as described above. The EAB will play a key role in monitoring adherence to the trial protocol and ensuring research quality as well as prompt and accurate reporting of adverse events.

EXPECTED OUTCOMES OF THE STUDY

The expected outcomes are a reduction in the incidence of psychiatric diagnoses at 6-month follow-up, and a general improvement in mental health symptoms, psychological functioning, well-being, and economic outcomes at each assessment, in refugees in the SH+ intervention arm, as compared to ETAU.

DISSEMINATION OF RESULTS AND PUBLICATION POLICY

A detailed dissemination and communication plan will be developed by WHO in collaboration with project partners. The plan will be circulated across the study sites for comments and final approval.

Local Community

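### The annual cost is built from the baseline and 6-month CSSRI-EU, so it counts service use before randomisation and leaves out months 7 to 12

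*Protocol*

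**What the plan says.** Under Cost-effectiveness analysis (CSSRI), the Protocol says that a year's resource use is "assessed by means of completing the adapted CSSRI-EU at baseline and at 6-month follow-up". It then forms the yearly figure as follows: "Six months costs from the two surveys will be added to annual costs". No other survey is named there. The cost feeds the ICER and the net monetary benefit, which is computed "for a MWTP range between UK£ 0 and 50,000 in increments of UK£ 5,000".

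Other sections set different time points:

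- Analysis of the secondary outcomes lists the cost outcome as "CSSRI-EU (adapted) at 6 and 12 months of follow-up".
- Trial phase assessment schedules the instrument at the last visit: "12-month follow up: GHQ-12, M.I.N.I., WHODAS 2.0, PHQ-9, WHO-5 Wellbeing index, PSYCHLOPS, PMLD, PCL-5, EQ-5D-3L, and CSSRI-EU (adapted". Table 1 agrees and has both the CSSRI-EU and the EQ-5D-3L at baseline, 6 and 12 months.
- Trial phase assessment times the visits "at baseline (before random allocation), post-intervention (0-1 week after intervention), and at 6- and 12- months after randomization".
- Cost-effectiveness measures describes the CSSRI as a retrospective record of service use. The text gives no recall length.

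**The concern.** A retrospective survey completed before allocation cannot record anything that the intervention caused. If it supplies one of the two halves of the yearly cost, that half says nothing about SH+ against ETAU, and no survey is left to cover the second half of follow-up.

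Cost-effectiveness is part of the trial's stated objective, and lower health care cost in the SH+ arm is its third hypothesis. A cost that ends at month 6 but is labelled annual would miss any saving or added service cost that appears later. It could also be paired with QALYs over 12 months, because the section fixes no QALY horizon and the EQ-5D-3L is collected at both 6 and 12 months.

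**Working it through.** The Protocol gives no cost figure to reproduce. The check counts calendar windows and then follows the omission through the formulas.

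**1. Windows relative to randomisation (month 0).** Six-month recall is inferred from the reference to six-month costs.

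| Surveys summed | Windows (months) | Before randomisation | Follow-up covered |
|---|---|---|---|
| Baseline + 6 months (as written) | -6 to 0, and 0 to 6 | 6 months | 6 of 12 (50%) |
| 6 + 12 months (as scheduled) | 0 to 6, and 6 to 12 | 0 months | 12 of 12 (100%) |

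The recall assumption does not drive the result. With 3-month recall the written windows are -3 to 0 and 3 to 6. With 12-month recall they are -12 to 0 and -6 to 6. Neither reaches beyond month 6.

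**2. Effect on the incremental cost.** Let the arm differences in service cost be 0 before randomisation (in expectation), d1 in months 0-6 and d2 in months 7-12. Let I be the one-off SH+ delivery cost, which falls within months 0-6.

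- As written: I + 0 + d1 = I + d1.
- Over 12 months: I + d1 + d2.
- Error in incremental cost: -d2.

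For example, with assumed service-cost differences, take d1 = +£100 and d2 = -£100, -£150 or +£50. The 12-month difference is then £0, -£50 or +£150, while the written rule returns +£100 each time.

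**3. Effect on net benefit and ICER, with the same QALY difference (dQALY) in both.** Incremental net benefit is MWTP × dQALY minus incremental cost. The written rule therefore differs from the 12-month value by d2 at every MWTP, and the ICER differs by d2/dQALY in absolute size. The omitted amount that moves the ICER by one £5,000 step is |d2| = 5,000 × dQALY. dQALY is not in the document, so the values are assumed:

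| dQALY (assumed) | Omitted d2 per participant | Per month over six months |
|---|---|---|
| 0.005 | £25 | £4.17 |
| 0.01 | £50 | £8.33 |
| 0.02 | £100 | £16.67 |
| 0.05 | £250 | £41.67 |

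**4. Share of the 12-month service-cost difference captured, d1/(d1 + d2), excluding delivery cost.**

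- d2 = 0: 100%.
- d2 = d1/2: 1/1.5 = 67%.
- d2 = d1: 1/2 = 50%.

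**5. Precision.** With equal variances and correlation rho between six-month periods, the SE of the written sum relative to the 6-month cost alone is sqrt(2(1 + rho)). This is 1.41, 1.61, 1.73 and 1.84 at rho = 0, 0.3, 0.5 and 0.7. The baseline half therefore adds noise but no bias to the 0-6 month difference. Under the same assumptions the 6 + 12-month sum has the same SE as the written sum (ratio 1.00), so moving to 12 months brings no gain in precision.

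**The case against.** The strongest reply is that this is a slip of drafting. The section wants a yearly cost from two six-month surveys, and the schedule has exactly two post-randomisation surveys, at 6 and 12 months. Duration of the project places the cost-effectiveness work in months 28-36, after 6-month follow-up ends at month 24 and overlapping 12-month follow-up, which ends at month 30. That is compatible with an intention to use the 12-month data. It may well be what was meant, but the sentence naming baseline and 6 months is then wrong and needs the same correction. Nor is this a detail left to the SAP. The Protocol names the surveys, and an SAP would have either to repeat the error or to contradict it.

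Four narrower points stand:

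- The error of d2 exists only against a 12-month target. Under a declared 6-month horizon, what remains is the added variance and the wrong label. The Protocol's own word is annual, which supports the 12-month target.
- The pound figures are arithmetic on assumed QALY gains and are no evidence that d2 is large.
- The inclusion of SH+ delivery cost in the ICER and net benefit is inferred. The Protocol names it in the cost-function paragraph, not in the list of costs for the incremental analysis. The argument that delivery is counted in full while later savings are not is plausible but not certain.
- The hope of better economic outcomes at every assessment, in Expected outcomes, is weak support, because neither economic instrument is given post-intervention. The listed 6- and 12-month cost outcome is enough without it.

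**Conclusion.** The concern holds. Followed literally, the rule yields a yearly cost of which 6 of 12 months predate randomisation (half of the months, not necessarily half of the cost), and in which months 7-12 do not appear. The expected incremental service cost is then the 0-6 month difference alone, and each arm's annual cost is mislabelled.

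Against a 12-month target, net benefit is wrong by d2 at every MWTP and the ICER by d2/dQALY. Neither d2, in size or direction, nor dQALY is in the document, so the actual distortion cannot be stated. At gains of 0.005 to 0.05 QALY, £25 to £250 per participant is enough to move the ICER by £5,000. The six-month recall is inferred, but the loss of months 7-12 does not depend on it. The primary outcome is unaffected and all the needed data are already scheduled. This should be fixed before the economic analysis.

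**What to change.** Rewrite the resource-use sentences under Cost-effectiveness analysis (CSSRI) to agree with the assessment schedule and the list of secondary outcomes:

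- State that the adapted CSSRI-EU is completed at baseline, 6 and 12 months, and give its recall period as six months if that is what the adapted form uses.
- Define the 12-month cost as the sum of the 6- and 12-month survey costs plus SH+ delivery cost, with QALYs over the same 0-12 months.
- Exclude baseline cost from the outcome. It can serve as a covariate in the net-benefit regression. This is advisable but not needed to correct the error.

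If a 6-month horizon is intended, use the 6-month survey cost alone plus SH+ delivery cost, take QALYs over 0-6 months, and drop the word annual.

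The cost is two or three sentences of Protocol text. No new data collection is needed, since both economic instruments are already scheduled at baseline, 6 and 12 months.
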